### 4.2.1. Primary Objective

The primary objective is to confirm that the Medtronic Hugo™ RAS System performs as intended when used for prostatectomy or cholecystectomy. Primary endpoint is below:

- Completion rate: A proportion of subjects who completed the surgery without conversion (to open or conventional laparoscopic surgery) due to system serious malfunction, and without any major complications within 24-hour post-surgery
  - \* Major complication is defined as Clavien-Dindo grade  $\geq 3$

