## 6.5. Sample Size Determination

To estimate the number of sample size, two things are taken into account: The number of subjects from previous studies, and the minimum number [8] to show whether the primary objective is met. We plan to include 40 patients for the study.

- Research hypotheses: The completion rate is greater than or equal to 95% (point estimate).

The completion is defined that surgery completion without conversion (to laparoscopic or open surgery) due to system serious malfunction, and without any major complications within 24-hour post-surgery. Therefore, when a subject who inevitably converted not due to the Hugo™ RAS system, it is not considered as a surgery failure as per the definition and the subject will be excluded from the primary endpoint analysis. Also, a complication within 24-hour post-surgery will not be considered as a surgery failure unless it falls under the definition of major complication.

According to previous literature on adverse events in robotic surgeries over 14 years using da Vinci, the average rates of device malfunctions and failure-related conversions was 3% (varied between 0.4% and 8.0%) and 0.9% (varied between 0.1% and 2.7%), respectively [9]. In Korea, the reported rate of system malfunctions and failures was less than 2% among over 10,000 da Vinci robotic procedure cases between 2005 to 2013. However, no cases of malfunction led to conversion to open or laparoscopic surgery [10].

---

 According to the Korean Clinical Practice Guideline for the Treatment of Prostate Cancer (The Korean Urological Oncology Society, 2020)[7], radical prostatectomy is an appropriate therapy for any patient with clinically localized prostate cancer that can be completely excised surgically, who has a life expectancy of  $\geq 10$  years, and who has no serious comorbid conditions that would contraindicate an elective operation.

 Relative contraindications for laparoscopic cholecystectomy include followings: Inability to tolerate general anesthesia due to cardiopulmonary diseases, hemodynamic instability, pregnancy (3rd trimester), malignant tumors, liver cirrhosis and portal hypertension, and intestinal adhesions (Kim & Seo. Hepato-Biliary-Pancreatic Surgery (4th ed.). 2019)

  $N \geq 30$  according to the central limit theorems

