### 7.3. Rationale

This trial will collect patient data undergoing two representative procedures (i.e., prostatectomy, cholecystectomy) in robotic surgery field to minimize potential confounding effect due to surgeon's proficiency or learning curve.

The study is designed as single-arm trial due to following logistics issues: Room to setup the investigational device, space for storage, and the number of commercialized products at the study site.

The primary endpoint of this study is the completion rate, which is defined as a proportion of subjects who completed the surgery without conversion due to system serious malfunction, and without any major complications within 24-hour post-surgery. Recent pivotal trial approved from the MFDS also utilized completion rate as the primary endpoint [11, 12].

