### 8.10. Assessment of Effectiveness

Effectiveness of the Hugo™ RAS System will be evaluated through the study primary endpoint (completion rate). Effectiveness assessment will be done on the day of surgery as below.

*Medtronic Business Restricted*

- Completion rate: A proportion of subjects who completed the surgery without conversion due to system serious malfunction, and without any major complications within 24-hour post-surgery

Surgery completion is defined if procedure is completed without conversion to open or laparoscopic surgery due to system serious malfunction per surgery record, and no major complication reported within 24-hour post-surgery period. Note that unavoidable Aes are inherent to the procedure (see Section 10.2 for details) are not included in this definition of major complication within 24-hour post-surgery.

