***Medtronic Business Restricted***

## 9. Statistical Design and Methods

### 9.1. General Aspects of Analysis

The study analysis will occur after all patients complete the 30-day follow-up and data entry error or non-reasonable values are cleaned. Data analysis will be performed by Medtronic or its designee using SAS for Windows (version 9.4 or higher, SAS Institute Inc. Cary, NC) or other widely accepted statistical or graphical software.

Statistical tests will be conducted at a two-sided alpha level of 0.05. Confidence intervals will be presented as 95% confidence intervals.

The following populations will be considered for the analysis of data for this study:

- Full Analysis Set (FAS): The full analysis set is defined as all enrolled subjects in whom the Hugo™ RAS procedure is begun (defined as the first skin incision). In the event that a subject is consented but the first incision does not occur (e.g., if the subject becomes ineligible during the timeframe between consent and the procedure day), that subject will be excluded. Also, a subject who inevitably converted (to open or conventional laparoscopic surgery) not due to the Hugo™ RAS system will be included in the safety and other descriptive analyses but excluded from the primary endpoint analysis (since the subject is not evaluable).
- Per Protocol Set (PPS): The per protocol set is a subset of the FAS including only those without any major protocol deviations. Following subjects from the FAS will be excluded from the PPS:
  - Subject who inevitably converted (to open or conventional laparoscopic surgery) not due to the Hugo™ RAS system
  - Subject did not meet Inclusion/exclusion criteria
  - Subject chooses to withdraw
  - Failure to collect required study data up to 30-day post-surgery

The FAS will be the primary analysis set for the evaluation of the primary and secondary endpoints. Statistical analysis will be performed for each analysis set. However, if all subjects complete the study per the CIP, the results can be presented regardless of the analysis set.

Subject disposition will be illustrated in a CONSORT diagram. All enrolled subjects will be included in a subject disposition table indicating reasons for exclusion from the FAS and PPS analysis sets.

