**Table 7. Adverse Event and Device Deficiency Definitions**

General	
Adverse Event (AE)*	
Any untoward medical occurrence, unintended disease or injury, or untoward clinical signs (including abnormal laboratory findings) in subjects, users or other persons, whether or not related to the investigational medical device and whether anticipated or unanticipated.
 
NOTE 1: This definition includes events related to the investigational medical device or the comparator. NOTE 2: This definition includes events related to the procedures involved. NOTE 3: For users or other persons, this definition is restricted to events related to investigational medical devices or comparators. (ISO 14155:2020 section 3.2) *The ISO 14155 definition is equivalent to AE under KGCP Article 2 item M.

Adverse Device Effect (ADE)*	
Adverse event related to the use of an investigational medical device
 
NOTE 1: This definition includes adverse events resulting from insufficient or inadequate instructions for use, deployment, implantation, installation, or operation, or any malfunction of the investigational medical device. NOTE 2: This definition includes any event resulting from use error or from intentional misuse of the investigational medical device. NOTE 3: This includes 'comparator' if the comparator is a medical device. (ISO 14155:2020 section 3.1) * The ISO 14155 definition is equivalent to ADE under KGCP Article 2 item N.

Unanticipated Adverse Device Effect (UADE)	
Deviation from the aspect of ADEs or the degree of harm reflecting from the available medical device related information such as investigator's brochure or medical device package insert (KGCP Article 2 item P)

Device Deficiency (DD)	
Inadequacy of a medical device with respect to its identity, quality, durability, reliability, usability, safety or performance
 
NOTE 1: Device deficiencies include malfunctions, use errors and inadequacy in the information supplied by the manufacturer including labeling. NOTE 2: This definition includes device deficiencies related to the investigational medical device or the comparator. (ISO 14155:2020 section 3.19)

Relatedness	
Study Device	
An AE that results from the presence or performance of any component of the system and its compatible components

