7.9 Evaluation of Objectives

Study objectives will be assessed through study endpoints measurement.

- Primary Endpoint

The primary objective is to confirm that the Medtronic Hugo™ RAS System performs as intended when used for prostatectomy or cholecystectomy. Primary endpoint is below:

- Completion rate: A proportion of subjects who completed the surgery without conversion (to open or conventional laparoscopic surgery) due to system serious malfunction, and without any major complications within 24-hour post-surgery (Major complication is defined as Clavien-Dindo grade ≥ 3)

The number of subjects successfully completed the surgical procedure, percentage, and its Clopper-Pearson Exact 95% confidence interval will be summarized. If the point estimate of the completion rate is greater than or equal to the pre-determined value (i.e., 0.95), it is considered that the primary objective is met. This primary endpoint will be assessed on overall subjects and according to surgery performed (prostatectomy and cholecystectomy).

- Secondary Endpoints

The secondary objective is to assess the short-term safety outcome of the Medtronic Hugo™ RAS System when used for prostatectomy or cholecystectomy. Secondary endpoints are below:

- Overall complication rate through 30-day post-surgery: A proportion of subjects with any postoperative complication within 30-days post-surgery using the investigational device
- Major complication rate through 30-day post-surgery: A proportion of subjects with any postoperative complication classified ≥ 3 by the Clavien-Dindo system within 30-days post-surgery using the investigational device
- Readmission rate through 30-day post-surgery: A proportion of subjects hospitalized within 30 days post-surgery
- Reoperation rate through 30-day post-surgery: A proportion of subjects go through reoperation for the same indication within 30 days post-surgery
- Device deficiency rate: A proportion of subjects with any device deficiency (DD) during robotic assisted surgery using the investigational device

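### The failure and exclusion rules for conversions are not complementary, so a Hugo-caused conversion without a serious malfunction can be counted as a completed surgery

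*Protocol*

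**What the plan says.** The objective in Protocol 4.2.1 is broad: "The primary objective is to confirm that the Medtronic Hugo™ RAS System performs as intended when used for prostatectomy or cholecystectomy". The endpoint under it is narrower.

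- **Failure rule.** Section 8.10 states: "Surgery completion is defined if procedure is completed without conversion to open or laparoscopic surgery due to system serious malfunction per surgery record". A major complication within 24 hours is the other way to fail. The same cause appears in the Synopsis, 4.2.1, 6.5 and 7.3, and in SAP 6 and 7.9, where the wording is "without conversion (to open or conventional laparoscopic surgery) due to system serious malfunction". Neither document says what makes a malfunction serious, and Protocol section 11 provides no review committee.
- **Exclusion rule.** Protocol 9.1 (repeated in SAP 7.1.3) takes out of the primary analysis "a subject who inevitably converted (to open or conventional laparoscopic surgery) not due to the Hugo™ RAS system". Section 6.5 puts it as "when a subject who inevitably converted not due to the Hugo™ RAS system, it is not considered as a surgery failure" and allows such subjects to be replaced until 40 is reached.
- **Success rule.** The objective is met if the point estimate is at least 0.95 (Protocol 9.1, 9.4; SAP 7.9). Section 6.5 translates this into no more than 2 of 40 subjects falling short.

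Section 8.5 records every conversion to open or laparoscopic surgery with its reason, and 9.3 summarises conversions descriptively.

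**The concern.** One rule turns on serious malfunction and the other on whether the system was the cause. Between them lies a conversion that the system caused without a serious malfunction: an arm conflict that cannot be resolved, inadequate reach or view, an instrument that cannot do the task, or a lesser fault that the surgeon decides not to wait out.

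The documents make this class plausible. Section 5.6.4 anticipates arms colliding. Table 2 lists field of view, workspace and redocking effort among its acceptance criteria. Table 7 takes a wide view of device inadequacy: "Device deficiencies include malfunctions, use errors and inadequacy in the information supplied by the manufacturer including labeling".

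A subject whose robotic operation was abandoned because of the device is the kind of case that an endpoint on intended performance should catch. If the rule allows that subject to count as completed, the error favours the device, in an unblinded single-arm trial whose result can turn on one subject.

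**Working it through.** **1. The plan's own figure.** Inputs: n = 40 and threshold 0.95 (Protocol 6.5, 9.4). 0.95 × 40 = 38, so at least 38 completions and at most 2 failures. This agrees with 6.5.

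**2. The two rules side by side.**

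| Conversion to open or laparoscopic surgery | Failure rule (8.10) | Exclusion rule (6.5, 9.1) | Result |
|---|---|---|---|
| Caused by a serious system malfunction | applies | does not apply | failure |
| Inevitable, not caused by Hugo | does not apply | applies | excluded, replaceable |
| Caused by Hugo, no serious malfunction | does not apply | does not apply | completed, if 8.10 is read literally |

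A conversion that Hugo did not cause but that was not inevitable also meets neither rule. All rows assume no major complication within 24 hours, which would be a failure for any subject in the primary analysis.

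**3. One subject, three readings.** Take 2 counted failures, 1 subject in the third row and 37 clear completions.

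- Completed (literal 8.10): 38/40 = 95.0%, met.
- Called not due to Hugo and excluded: 37/39 = 94.9%, not met; once replaced by a subject who completes, 38/40 = 95.0%, met.
- Failure: 37/40 = 92.5%, not met.

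With no counted failures, three such conversions are needed: 40/40 as written against 37/40 = 92.5% if they count.

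**4. Chance of meeting the rule.** Let f be the counted-failure rate and g the rate of Hugo-caused conversions without a serious malfunction. Both are assumptions; the documents give no value for g. The chance of success is P(X ≤ 2) = Σ C(40,k) p^k (1−p)^(40−k) over k = 0, 1, 2, with p = f under the literal rule and p = f + g if these conversions count as failures. For f = 0.02 the terms are 0.4457 + 0.3638 + 0.1448 = 0.954.

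| f | literal rule, any g | g = 1% | g = 3% | g = 5% |
|---|---|---|---|---|
| 2% | 0.954 | 0.882 | 0.677 | 0.463 |
| 0.9% | 0.994 | 0.960 | 0.796 | 0.577 |

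The 0.9% row borrows the average failure-related conversion rate that 6.5 quotes for another device and assumes no major complications.

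**The case against.** The best defence is that 8.10 should not be read alone. If the absence of a serious malfunction were enough for success, the exclusion in 6.5 and 9.1 would be unnecessary. Section 6.5 says instead that completion cannot be assessed when Hugo was not the cause. That suggests a two-way split: caused by Hugo, hence a failure; not caused by Hugo, hence not evaluable. Since seriousness is undefined, a fault that forces conversion might also qualify as serious. This is a fair reading, so scoring as completed is what the literal text gives and not a rule that the plan states. But the documents then support different answers for the same subject, and two of the three readings never produce a failure.

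A reader might infer more in three places.

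- **That the endpoint cannot answer the objective.** This is too strong. It still captures serious-malfunction conversions and 24-hour major complications. Conversion reasons are recorded, and the device deficiency rate is a secondary endpoint. None of that descriptive information enters the success rule, however.
- **That a switch to another robot is scored as completed.** The documents are silent. Section 7.3 mentions "the number of commercialized products at the study site" only as a logistical reason for the single-arm design, and 8.5 has no field for such a switch.
- **That the cadaveric work already treated view and workspace as grounds for failure.** In Table 2 procedure failure rests on an unresolved malfunction; view and workspace are separate customer requirements.

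The endpoint was also matched to an earlier pivotal trial, and 6.5 uses that match in justifying the sample size. The precedent is a reason to keep reporting the present version, but it does not close the gap.

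**Conclusion.** The point holds as a defect in the endpoint definition. The rules do not cover every conversion, the central term is undefined, and the SAP repeats the gap. The size that needs no assumed rate is the single subject who decides between 92.5% and 95.0% when two failures have already been counted. The probabilities in the second table show sensitivity only. The published conversion rates in 6.5 concern failure-related conversions with another device and neither support nor bound g. If no such conversion occurs, the primary result is unaffected; but a classification chosen after the results are known, in an open trial, would carry little weight.

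**What to change.** Align the Synopsis, Protocol 4.2.1, 6.5, 7.3, 8.10 and 9.1, and SAP 6, 7.1.3 and 7.9, on one complementary rule:

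- **Failure:** conversion to open or laparoscopic surgery for any reason attributable to the Hugo system or its compatible components, including a malfunction of any grade or a device deficiency that caused the conversion; or a major complication within 24 hours, as now.
- **Not evaluable:** every other conversion, whether the cause lies with the patient, the anaesthetic, the facility or the surgeon's choice. Drop the condition that it be inevitable.
- **Attribution:** taken from the recorded reason for conversion.

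Add two sensitivity analyses. One keeps the present serious-malfunction version, with that term defined, for comparability with the earlier pivotal trial. The other counts every conversion as a failure, which needs no judgement about cause.

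State how a switch to another robotic system is classified, and add that option to the conversion field.

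The cost is a wording amendment to both documents and one extra response option; the reason for conversion is already collected. The completion rate may be slightly lower, and the primary endpoint would match the earlier trial less directly.

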## 8.11. Assessment of Safety

Safety will be assessed by monitoring the occurrence of Aes and DDs. AE assessments will take place starting with the point of consent through study exit and will be recorded in the CRF. The secondary endpoints of this study (i.e., complication rate and readmission/reoperation rate (through 30-day post-surgery), DD rate) will assess the safety of the investigational device. See Section 10 for further information on the collection of safety information.

## 8.12. Recording Data

Data collected on each subject will be recorded on a web-based electronic case report form (eCRF). The electronic data capture system maintains an audit trail on entries, changes or corrections in the CRFs. Instructions for proper completion of the CRF will be provided to the site at the start of the study. The investigator must ensure accuracy, completeness and timeliness of the data in the CRFs. CRFs shall be signed by the principal investigator or a delegated investigator (physicians only).

Data entered must be traceable to source documents. The investigator must ensure the availability of source documents from which the information on the eCRFs was derived. Source documents, which may include subject medical records, clinical charts, procedure reports, and laboratory notes, must be created and maintained by the investigational study site team. The type and location of source documents should be documented. Where printouts of electronic medical records, are provided as source documents, or where copies of source documents are retained as source documents, those should be certified. Certification must contain (1) the signature of the individual making the copy, (2) the date the copy was made and (3) a statement attesting to the accuracy and completeness of the copy.

In general, eCRFs (or paper copies) may not serve as source documents. For data elements not routinely captured in medical records, the study site may use source document worksheets if identified as source documents. On the other hand, the CRF may be considered source for the following data collection elements:

- Enrollment status: Study site assigned subject reference, study exit, reason for exit
- Adverse event: Date study site became aware of event, severity, Clavien-Dindo grade, relatedness
- Device deficiency: Date study site became aware of event
- Study deviations: Reason for deviation

The source documents must be made available for monitoring or auditing by Medtronic's representative or representatives of the competent authorities and other applicable regulatory agencies.

## 8.13. Deviation Handling

A study deviation is defined as an event within a study that did not occur according to the Clinical Investigation Plan (CIP) or the Clinical Trial Agreement (CTA). Prior approval by the sponsor of deviation is expected unless when a deviation is necessary to protect the safety, rights or well-being of a subject in an emergency or in unforeseen situations beyond the investigator's control (e.g., subject failure to attend scheduled follow-up visit, inadvertent loss of data due to computer malfunction, inability to perform required procedures due to subject illness). All study deviations must be reported on the CRF regardless of whether medically justifiable, preapproved by the sponsor, an inadvertent occurrence, or taken to protect the subject in an emergency.

In the event the deviation involves a failure to obtain a subject's consent, or is made to protect the life or physical well-being of a subject in an emergency, the deviation must be reported to the IRB as well as sponsor within five working days. All other study deviations must be reported to the sponsor as soon as possible upon the study site becoming aware of the deviation, per IRB policies and/or local laws.

The sponsor is responsible for analyzing deviations, assessing their significance, and identifying any additional corrective and/or preventive actions (e.g., amend the CIP, conduct additional training, terminate the investigation). Repetitive or serious investigator compliance issues may result in initiation of a corrective action plan with the investigator and study site, and in some cases, may necessitate suspending enrollment until the problem is resolved or ultimately terminating the investigator's participation in the study.

Examples of major study deviations include but are not limited to:

- Failure to obtain proper IC
- Subject did not meet Inclusion/exclusion criteria
- Failure to collect required study data up to 30-day post-surgery

Other minor deviations shall be recorded along with reason for deviation. Subjects with minor deviation only may not be excluded from the final analysis unless the deviation affects the study outcome.

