### 7.2. Design

This study is a prospective, single-center, single-arm, pivotal trial in 40 patients undergoing prostatectomy (20) or cholecystectomy (20) using the Medtronic Hugo™ RAS System. Subjects will be followed for 30 days post procedure. As this study is a single-arm trial, no randomization or blinding will be applied.

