7.1.2 Clinical Investigation Plan (CIP) Deviations

Subjects with protocol deviations will be summarized and protocol deviations will be reported by type on overall FAS subjects and distinguishing minor and major protocol deviations/violations. Major protocol deviations and violations will be defined and identified by the study team prior to run statistical analysis, based on protocol deviations listing provided by statistician.

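### Protocol 8.13 lets a minor deviation remove a subject from the final analysis on an undefined test tied to outcome, contradicting the analysis sets in Protocol 9.1 and SAP 7.1.3

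*Protocol*

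**What the plan says.** **Deviation handling (Protocol 8.13).** Three kinds of major deviation (improper consent, ineligibility, missing required data to day 30) are introduced with "Examples of major study deviations include but are not limited to". On the rest, the section says: "Subjects with minor deviation only may not be excluded from the final analysis unless the deviation affects the study outcome". It also says: "The sponsor is responsible for analyzing deviations, assessing their significance".

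**Analysis sets (Protocol 9.1, repeated in SAP 7.1.3).** The FAS is every enrolled subject with a first skin incision. Its one carve-out is a conversion not caused by the system: that subject stays in the safety and descriptive analyses but leaves the primary endpoint analysis. "The FAS will be the primary analysis set for the evaluation of the primary and secondary endpoints", and 9.1 applies the 0.95 success threshold in the FAS. The PPS is the FAS without major deviations, with four listed exclusions: conversion not due to the system, ineligibility, withdrawal, and missing required data to day 30.

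**Classification (SAP 7.1.2).** "Major protocol deviations and violations will be defined and identified by the study team prior to run statistical analysis, based on protocol deviations listing".

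**Setting.** Protocol 7.2: "As this study is a single-arm trial, no randomization or blinding will be applied". Protocol 9.1: "The study analysis will occur after all patients complete the 30-day follow-up".

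**The concern.** The exception in 8.13 belongs to neither analysis set. It concerns minor deviations, so it is not the PPS rule in 9.1. It speaks of the final analysis without qualification, so on its face it reaches the FAS, where 9.1 allows no exclusion for deviations. Someone deciding whether to keep a subject could cite 8.13 for removal and 9.1 for retention.

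The criterion is also loose. Deciding whether a deviation affected the outcome invites looking at that outcome. The text does not define the effect or say when the decision is made. It does give the sponsor the task of weighing deviations, in a trial with no blinding and no data review committee (Protocol 11). The success rule allows two failures in 40, so a very small number of removals could change the result.

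**Working it through.** **1. The passages compared.**

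| | Set named | Minor deviation can exclude? | Major deviation can exclude? |
|---|---|---|---|
| Protocol 8.13 | none (final analysis) | yes, under the exception | implied, set not stated |
| Protocol 9.1 / SAP 7.1.3, FAS | FAS | no | no |
| Protocol 9.1 / SAP 7.1.3, PPS | PPS | no | yes, plus four listed reasons |

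The 8.13 exception matches no row below it.

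**2. The plan's own figure.** Inputs are N = 40 and a threshold of 0.95 (Protocol 6.5 and 9.1). With f failures, success needs (N − f)/N ≥ 0.95.
- f = 2: 38/40 = 95.0%, pass.
- f = 3: 37/40 = 92.5%, fail.

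This reproduces the limit of two failures in 40 given in Protocol 6.5.

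**3. Effect of removing d failures from the FAS without replacement.** Success needs (N − f)/(N − d) ≥ 0.95.
- N = 40, f = 3, d = 1: 37/39 = 94.87%, still a fail.
- N = 40, f = 3, d = 2: 37/38 = 97.4%, pass.
- N = 41, f = 3, d = 0: 38/41 = 92.7%, fail.
- N = 41, f = 3, d = 1: 38/40 = 95.0%, pass.

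The case of 41 is possible because Protocol 6.1 sets 40 as a minimum. Removal can also hurt: from 38/40, dropping one completer gives 37/39 = 94.87%, a fail.

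**4. Effect on the chance of passing.** The documents give no true rate for this purpose and no number of removals, so both are assumptions. The figures are worst-case bounds: they suppose that every failure needed for a pass carries a minor deviation and is removed. The pass probability is the binomial probability that the number of failures does not exceed the largest passing f.

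| Evaluable | Removals allowed | Largest passing f | True rate 0.85 | 0.90 | 0.95 |
|---|---|---|---|---|---|
| 40 | 0 | 2 | 4.9% | 22.3% | 67.7% |
| 40 | 1 | 2 | 4.9% | 22.3% | 67.7% |
| 40 | 2 | 3 | 13.0% | 42.3% | 86.2% |
| 41 | 0 | 2 | 4.3% | 20.9% | 66.3% |
| 41 | 1 | 3 | 11.8% | 40.3% | 85.3% |

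**5. SAP 7.1.2.** Major deviations determine only the PPS, so none of the figures above can arise through this section. Its weakness is narrower. The study team both defines and identifies the category from a listing of deviations that have already occurred. The two protocol lists it would draw on also differ: improper consent is major in 8.13 but is not among the four PPS exclusions in 9.1.

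**The case against.** The best defence is that 8.13 is an operational section whose default is to keep the subject, while 9.1 and SAP 7.1.3 define the analysis sets and should govern. SAP version 2.0 (26 April 2023) is later than protocol V6.0 (3 April 2023). It repeats the FAS definition and does not carry the exception over. On this view the sentence means only that a minor deviation which spoils outcome assessment may be treated like a major one, for the PPS. The synopsis gives that some support, since it describes the PPS loosely as subjects who completed the study according to the plan. Protocol 9.1 also requires a disposition table giving reasons for exclusion from each set, so a removal from the FAS would be visible.

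Much of this stands. The benign reading is available, and 8.13 does not make exclusion depend on whether the subject completed. But the text does not state the benign reading, and no document says that 9.1 overrides 8.13. The disposition table would disclose a removal without preventing it.

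Four stronger readings are tempting but not supported:
- *That the SAP leaves major deviations to be defined after outcomes are known.* SAP 7.1.2 says before the statistical analysis is run, from a deviations listing. That the team may know outcomes by then is a fair inference from an unblinded trial with a 24-hour endpoint, but the SAP does not say it. Nor is the category blank, given three examples in 8.13 and four exclusions in 9.1.
- *That this SAP rule can change the trial's result.* It bears on the PPS, and success is decided in the FAS.
- *That one removal is enough at the planned size.* From 37/40 it is not.
- *That a removed non-completer could be replaced by a completer.* Protocol 6.5 allows new enrolment only for conversions not due to the system.

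**Conclusion.** Wrong as written: an internal contradiction that should be corrected. Protocol 8.13 permits an exclusion that the set definitions in 9.1 and SAP 7.1.3 do not allow, on a criterion nobody has defined.

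The primary result is exposed only if 8.13 is applied to the FAS. In that case two removals from three failures at N = 40, or one removal from three at N = 41, turn a fail into a pass. At an assumed true rate of 0.90, the worst-case chance of passing rises from 22.3% to 42.3% (40 subjects, two removals) or from 20.9% to 40.3% (41 subjects, one removal). Nothing in the documents shows an intention to use the clause this way. The SAP 7.1.2 point is secondary and confined to the PPS.

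**What to change.** 1. In Protocol 8.13, delete the exception that begins with the word unless.
2. In Protocol 8.13 and 9.1 and SAP 7.1.3, state that no protocol deviation removes an enrolled (consented), incised subject from the FAS, and that exclusions for deviations apply to the PPS only. The existing rule for conversions not due to the system is a separate matter and is not changed by this edit. The word consented is needed because enrolment is defined by consent (Protocol 6.2 and 8.3).
3. For the PPS only, have SAP 7.1.2 say that major deviations are identified against one closed list, signed off before endpoint data are tabulated. Pointing to the 9.1 list alone would not do, because it omits the consent failure named in 8.13. The two lists must be reconciled first.

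The cost is a few sentences in each document and the amendment step. The sample size of 40, the limit of two failures, the data collected and patient procedures do not change. With the fix, three failures in 40 stays at 37/40 = 92.5% and the objective is not met.
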